## **10.0 CRITERIA FOR EVALUATION AND ENDPOINT DEFINITIONS**

The primary endpoint of this study is histologically proven presence/absence of carcinoma of the prostate after seven years.

- 10.1 Survival is defined as the period of time between Final Enrollment and death of any cause.
- 10.2 Prostate cancer-specific survival is defined as the period of time between Final Enrollment and death due to prostate cancer. For staging criteria, see Section 19.2.
- 10.3 Criteria for Estimation of Performance Status: At the First Visit participants will be graded according to the current Southwest Oncology Group grading scale:

### **GRADESCALE**

0	Fully active; able to carry on all normal activities without restriction.
1	Restricted in physically strenuous activity but ambulatory and able to carry out work of a light or sedentary nature, e.g., light housework, office work.
2	Ambulatory and capable of all self-care but unable to carry out any work activities. Up and about more than 50% of waking hours.
3	Capable of only limited self-care; confined to bed or chair more than 50% of waking hours.
4	Completely disabled. Cannot carry on any self-care. Totally confined to bed or chair.

NOTE: If the participant has a permanent disability that does not impair his ability to carry on all normal activities of daily living, he may be graded with a Performance Status of 0.

## **11.0 STATISTICAL CONSIDERATIONS**

- 11.1 OVERVIEW: The primary objective of this prevention trial is to assess whether participants randomized to receive finasteride for seven years will have a different proportion of prostate cancer than participants randomized to receive a placebo for seven years. Other objectives of this study are listed in the Objectives section of this protocol (Section 1.0) and include estimation of the side-effect rates associated with finasteride, assessment of the acceptability of long-term finasteride use by healthy participants, and assessment of the effect of finasteride on the sensitivity and specificity of DRE and PSA.

A study of 18,000 randomized subjects (9,000 placebo, 9,000 finasteride) is planned. The trial will be double-blind. The participants to be enrolled will be 55 years old, generally healthy, have a normal PSA, and be free of significant chronic comorbid disease, especially severe symptoms of BPH.

The participants randomized will be scheduled for prostate biopsy following seven years of study treatment. The primary outcome is the presence or absence of prostate cancer as assessed by the end-of-study biopsy or prior to seven years on study.

It is projected that accrual will be completed in three years, with approximately 3,600 subjects (20%) randomized in the first year and approximately 7,200 subjects (40%) in each of years two and three. It follows that the last biopsy will be completed ten years following the beginning of enrollment.

The validity of this study depends on a number of CRITICAL ASSUMPTIONS related to the ability to know when a participant is not adherent, between arm comparability for the

participants who do not have a seven year biopsy, the mathematical form of the relationship of finasteride's effect on PSA levels, finasteride's effect on DRE and TRUS sensitivity, and the size of finasteride's effect in preventing BPH. (The CRITICAL ASSUMPTIONS are identified and discussed subsequently.) These CRITICAL ASSUMPTIONS are necessary because of finasteride's effect on the size of the prostate gland and particularly the tendency for finasteride to reduce PSA levels. The consequences of finasteride's effect on PSA are magnified by PSA's growing importance as a marker for prostate cancer incidence. In general terms, the intervention under study affects an important diagnostic test for the detection of the disease under study. These CRITICAL ASSUMPTIONS are necessary despite the design compromises made to accommodate finasteride's effect on PSA as described in the Background section of this protocol (Section 2.0).

The study is planned for a 5% two-sided test and will have 90% or greater power to detect a 25% difference between the arms in the proportion of prostate cancers following seven years of study treatment. This power computation is based on the following parameters: the non-adherence in the finasteride arm does not exceed 10%, the placebo arm finasteride use does not exceed 5%, and at least 60% of the participants have the seven year biopsy. The anticipated loss of participants is due to refusal, loss to follow-up, or death.

There will be no interim analysis of the primary outcome because the primary outcome will not be known until the end of the study. There will be close monitoring of the study with respect to safety, mortality, side-effects, conformity to the trial planning parameters, and conformity to the CRITICAL ASSUMPTIONS.

- 11.2 BIOPSY PRIOR TO SEVEN YEAR BIOPSY: A special procedure will be implemented to maximize the likelihood that the participants having biopsies prior to their scheduled end-of-study biopsy, for example as a result of positive digital rectal examination or elevated PSA, are comparable between the arms in both numbers and characteristics. Specifically, the finasteride arm PSA biopsy threshold will be adjusted based on experience with finasteride-induced downward shift in the PSA distribution so that approximately the same number of participants will be biopsied due to PSA elevations as in the placebo arm. This procedure is necessary because of the effect of finasteride on lowering PSA levels. If this procedure were not used, that is, if unadjusted PSA values were used as the threshold for biopsy in the finasteride arm, then participants in the placebo arm would have a greater probability of having a biopsy prior to the scheduled seven year biopsy, and therefore the placebo arm would likely have more cancers detected because of the greater number of biopsies.

CRITICAL ASSUMPTION: It is assumed that the finasteride-induced PSA change results in a simple downward shift in the PSA distribution and therefore generally preserves the original ranking of the affected participants.

If the preceding assumption does not hold then there is no basis for an assurance that the finasteride arm PSA threshold control procedure will result in comparable participants in each arm being biopsied prior to the seven year biopsy. The validity of this assumption can be tested by comparing between the arms the characteristics of the participants selected for biopsy based on the PSA threshold. The characteristics compared can include: baseline PSA, race, age, body dimensions, medication adherence rate, quality of life measurements, AUA symptom score, etc.

- 11.3 ADHERENCE/CONTAMINATION AND PSA: Participants in the finasteride arm who take less study drug than allotted could have a PSA level declared as "elevated" due to medication nonadherence since their PSA levels may not be as depressed as participants who are fully adherent. Similarly, it is theoretically possible for participants in the placebo arm who take finasteride (placebo arm contamination) to have finasteride-induced lowered PSA levels which masks a prostate cancer. A finasteride contamination effect is also

possible in the finasteride arm. Therefore the degree of medication adherence and contamination must be known when performing PSA assessments. The plan is to assess adherence/contamination prior to obtaining PSA specimens and to defer taking a PSA specimen in cases where there is evidence of nonadherence or contamination until there is sufficient adherence and lack of contamination. Thus, the participant is motivated to become adherent and not take open label finasteride. Also, meaningless PSA results are avoided. This strategy requires the following assumption, however:

**CRITICAL ASSUMPTION:** The procedures used to assess adherence in the individual participant at each visit where a PSA specimen is to be obtained are sufficiently sensitive and reliable to detect degrees of nonadherence affecting PSA level interpretation.

- 11.4 **SEVEN YEAR BIOPSY:** It is assumed that approximately 40% of the randomized participants will not have a prostate biopsy following seven years of study treatment and have not had a positive biopsy prior to seven years of treatment. Specifically, it is assumed there will be a 40% loss to biopsy based on the sum of 20% mortality, 15% lost to follow-up, and 5% biopsy refusals. The 20% mortality is based on an assumption that the median age at study entry will be 63 years, with the seven year U.S. (white) all-causes mortality for men that age assumed to be approximately 20%. The 15% lost to follow-up is based on experience with other prevention trials. The 5% biopsy refusal rate is based on the belief that participants who stay on the study drug for seven years will be motivated to find out whether or not they have prostate cancer.

**CRITICAL ASSUMPTION:** It is assumed that the factors affecting loss to biopsy will operate the same in both arms of the study so that the groups of participants who do not have biopsies (deaths, lost, refusal) will be comparable between the arms.

Conformity to the above assumption can be monitored by comparing between the arms the characteristics of the participants who do not have the seven year biopsy and the reason for not having the biopsy.

- 11.5 **SENSITIVITY/SPECIFICITY OF DRE, TRUS, AND BIOPSY:** It is known that finasteride generally reduces the prostate gland size, and therefore has the potential to affect the sensitivity and specificity of DRE and TRUS; furthermore, finasteride could affect the sensitivity of the prostate biopsy. The directions and degrees of finasteride's effect on these sensitivities and specificities are unknown at this time, and will be investigated as part of this study. These possible sensitivity and specificity effects, if they exist, would seriously compromise the validity of this trial since the design of this trial had to be based on the following assumption:

**CRITICAL ASSUMPTION:** Finasteride does not affect the sensitivity or specificity of the DRE or the TRUS, nor does finasteride affect the sensitivity of the prostate biopsy.

- 11.6 **BPH AND TURP:** It is theoretically possible that the incidence of benign prostatic hypertrophy (BPH) prior to the seven year biopsy in the finasteride arm will be less than in the placebo arm due to the potential of finasteride to prevent BPH. If there are relatively more BPH incident cases in the placebo arm then it is possible that there will be relatively more transurethral resections of the prostate (TURP) in the placebo arm, from which it follows that there could be relatively more incidental prostate cancers found in the placebo arm through the use of TURP. The implementation of a procedure for balancing the numbers of TURPs between the arms is not planned because it would interfere too much with standard urological practice. Thus, there is potential for a bias of unknown magnitude in favor of the finasteride arm with respect to prostate cancer incidence prior to the seven year biopsy. This potential bias will not be corrected by the seven year biopsy unless the sensitivity of the seven year biopsy is equal to or exceeds the sensitivity of the interim TURPs, but the relationship of these sensitivities is not known at this time. If this TURP bias exists then this trial will be anticonservative. It follows that the following assumption is necessary:

**CRITICAL ASSUMPTION:** It is assumed that any bias resulting from TURPs in BPH incident cases will be negligible.

- 11.7 **ADHERENCE:** A three month enrollment period during which each participant is to take study medication (in this case placebo) is part of the design. Following the enrollment period medication adherence will be assessed and only participants with sufficient adherence will be randomized. The degree of "placebo effect" will also be assessed and be a basis for exclusion from randomization.

For participants who have a prostate cancer at the end of the study it is assumed that the degree of placebo arm finasteride contamination, designated  $d_0$ , will be approximately 0.05 (zero implies no contamination, one implies 100% contamination) and the degree of finasteride arm nonadherence, designated  $d_1$ , will be approximately 0.10 (zero implies complete adherence and one implies 100% nonadherence). These degrees of contamination and adherence ( $d_0$  and  $d_1$ ) are used as follows. Let  $p_0$  and  $p_1$  be the true prostate cancer probabilities for the placebo arm and finasteride arms, respectively. The seven year prostate cancer probabilities adjusted for the assumed adherence and contamination are  $p_{0r} = ((1 - d_0) \times p_0 + d_0 \times p_1)$  and  $p_{1r} = (d_1 \times p_0 + (1 - d_1) \times p_1)$  for the placebo and finasteride arms, respectively.

[figure not shown]
- 11.8 **PROBABILITY ASSUMPTIONS:** The true probability of detectable prostate cancer in the placebo group at seven years following study entry ( $p_0$ ) is assumed to be in the neighborhood of 6% (24,25).

The probability difference for seven years of treatment is defined as the difference of the true probability of prostate cancer at seven years in the finasteride arm minus the true probability of prostate cancer at seven years in the placebo arm, or  $p_1 - p_0$  (NB: a negative difference implies a finasteride benefit). This difference is can be multiplied by 100 and divided by  $p_0$ , that is  $100 \times (p_1 - p_0) / p_0$ , to give the percent difference due to finasteride. The probability difference adjusted for the assumed degrees of placebo arm contamination and finasteride arm nonadherence is  $p_{1r} - p_{0r}$  and this difference is also can be used as the adjusted percent difference due to finasteride, or  $100 \times (p_{1r} - p_{0r}) / p_{0r}$ .

- 11.9 **PRIMARY ANALYSIS:** The primary outcome analysis will consist of testing the coefficient of the arm indicator variable in a logistic regression model for the probability of prostate cancer. The logistic regression model will include covariates for all stratification factors except the Study Center. This analysis will include all subjects who have a biopsy at seven years plus the subjects who were found to have prostate cancer (histologically-proven) prior to seven years. The power computations which follow use standard formulas for computing the power when comparing proportions. The actual power of the trial is computed based on  $p_{0r}$  and  $p_{1r}$ , the probabilities adjusted for assumed degrees of contamination and nonadherence.

- 11.10 **POWER:** Based on 9,000 participants per arm, the graphs in Figure 4 illustrate actual power for an assumption of 60% of participants biopsied, true probability of prostate cancer in the placebo arm ( $p_0$ ) of 4% and 6%, unadjusted percent differences of 25% and 30%, and ranges for degrees of placebo arm contamination and finasteride arm nonadherence as described previously. If the desired actual power is 90% or above then the graphs in Figure 4 illustrate that this power is achievable provided: the unadjusted percent difference is 30%, the true probability of a positive biopsy in the placebo group ( $p_0$ ) is close to 6%, and the degree of placebo arm contamination and finasteride arm nonadherence do not become excessive. There is much less latitude for an unadjusted percent difference of 25%.

In particular, using the 60% biopsy rate, the power is 92.1% for an adjusted difference of 24.7% from a 6% placebo arm prostate cancer rate using a 5% placebo group contamination and a 14% finasteride arm nonadherence. This power computation is labeled in the fourth graph in Figure 4. These conditions are believed to be achievable if the trial is tightly controlled.

11.11 POWER FOR SIDE-EFFECTS AND ADVERSE EVENTS: The reported experience for one year of treatment with placebo (n=300) versus finasteride 5 mg (n=300) by the manufacturer includes the following:

	Finasteride	Placebo
decreased libido	4.7%	1.3%
ejaculatory disorder	4.4%	1.7%
impotence	3.4%	1.7%

The power using the first 1800 subjects per arm to detect differences in these measures (including a combined measure of sexual dysfunction) is shown below. The 1% one sided alpha level is used to permit five multiple comparisons at the 5% level.

placebo	side-effect percents		power
	placebo	finasteride	
1	1	2	.50
	1	3	.97
	1	4	.99
2	2	4	.86
	2	5	.99
	2	6	.99
5	5	8	.90
	5	10	.99
10	10	13	.67
	10	15	.99

11.12 CARDIOVASCULAR DISEASE: Because cardiovascular disease is common among the men of age 55 (eligibility ages of the participants to be enrolled) the power will be high to detect even small differences between the arms with respect to cardiovascular disease

incidence and events. For example, if the incidence rate for coronary artery disease (CAD) for participants on this study is estimated to be 25 per 1000 per year then there could be as many as 1575 diagnoses of CAD in the placebo arm, that is, 17.5% of the placebo arm participants. The 0.05 one-sided power to detect a 10% higher incidence of CAD in the finasteride arm (1733 incident cases or 19.3%) would be 91.4%.

- 11.13 **DATA AND SAFETY MONITORING:** An external Data and Safety Monitoring Committee (DSMC) will review the safety, mortality, side-effects, adherence, and potential violation of the assumptions necessary for trial validity. The DSMC will review unblinded trial monitoring data every six months.

The Data and Safety Monitoring Committee (DSMC) will be an independent panel of urologists, statisticians, epidemiologists, and ethicists (approximately 10 total members). PCPT Study Investigators will be excluded from membership in this committee, but may participate in the review of blinded data as necessary.

The DSMC will be provided with detailed reports of all adverse events and deaths, including summaries of hospitalization discharges and deaths.

Side-effect data will be monitored more closely for the first cohort of 3600 subjects than for those who follow. The purpose of this monitoring will be to confirm previous finasteride studies which claimed minimal side-effects. Adherence data will be reviewed in order to provide the opportunity to implement additional adherence measures.

A monitoring system for detecting deviations from the CRITICAL ASSUMPTIONS will be active throughout the trial. This system will be used to generate data for DSMC review. Because of the fragility of this trial with respect to conformity to CRITICAL ASSUMPTIONS, and the resulting complexity of the monitoring tasks, no specific stopping rules are specified.

- 11.14 **SECONDARY ANALYSES AND SECONDARY OBJECTIVES:** Beyond the analysis of the primary outcome described above, the probability of prostate cancer at seven years will be modeled using standard methods for categorical data, with explanatory variables including age, race, family history, gland size, laboratory data, etc. The probability of side-effects will be modeled using information on adherence (and other covariates).

Objective 1.2 (finasteride's effect on stage and grade) will be analyzed by comparing between the arms the grade and stage distribution of the incident cases. Data will come from pathology review of biopsy specimens. Standard categorical data analysis methods will be used.

Objectives 1.3, 1.4, 1.5, and 1.7 (toxicity, side-effects, mortality, BPH, and quality of life) will be analyzed by comparing between the arms the rates of events and magnitudes of effects. The data will come from reports of events, participant interviews, and side-effect and quality of life questionnaires. Standard categorical data methods, including methods for ordered categorical data will be used.

Objective 1.6 (finasteride's effect on screening modality) will require detailed pathology data as well as an analysis of the data generated from the procedures used to adjust PSA levels. Should finasteride prove to be efficacious in preventing prostate cancer then it will be important to be able to recommend to practitioners methods for monitoring for prostate cancer in those taking finasteride. Additional data addressing this issue may become available from trials of the use of finasteride in BPH.

Objective 1.8 (association of dietary fat and an increased risk of prostate cancer) will be approached as detailed in Appendix 19.7, which outlines methods of data collection and analysis.

Objective 1.9 (cohort study of CAG repeat length) will be approached as detailed in Appendix 19.8.

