**AMENDMENT #4**

The study referenced above has been amended as outlined below (additionally, [name] contact information was updated on the face page):

1. The Cardiovascular Assessments paragraph in Section 2.0 and Section 7.6 have been amended to better reflect the intent of the protocol regarding risk assessment.
2. Individuals previously diagnosed with Prostatic Intraepithelial Neoplasia (PIN) have been excluded from participation in this study. This is reflected in Section 5.6.
3. Section 6.1 has been amended to clarify that the factors outlined here are descriptive factors rather than stratification factors. Also, the age descriptive categories have been changed.
4. The Model Informed Consent Form has been amended as requested by the Data and Safety Monitoring Committee. Participants should be informed of this information as directed by your IRB.

The third paragraph of Section I has been replaced with three new paragraphs outlining storage of serum and tissue samples, and their possible use in future studies. The sixth paragraph of Section II has been amended to clarify that participants are "expected to" continue on the study for seven years. Section VII has been amended to soften the tone of Sentence 3 and indicate that access to medical records is voluntary. Section X has been amended to delete the last phrase of the second sentence. Finally, a box was added to the bottom of the form for participants to check if they do not wish to be contacted for future studies.

Replacement pages are enclosed for pages 18, 21, 22, 23, 42, 43 and 45 and should be inserted into your copy of the protocol.

This memorandum serves to inform the Statistical Center, CALGB and ECOG.

cc: PCPT Statistical Center Staff - [name]                      Axion Pharmaceuticals - [name]  
[name]    ECOG  
[name].    CALGB  
[name].  
[name].  
Merck, Sharpe and Dohme - [name]., Ph.D.

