#### **5.0 ELIGIBILITY CRITERIA**

##### **Enrollment Criteria**

- 5.1 Participants must be male, ages 55 or older. Participants must be of such an age and medical condition that the physician would anticipate treatment of a prostate tumor detected within seven years following study entry. If a participant would be of an advanced age or of an anticipated medical status such that diagnosed prostate cancer within seven years following study entry would not require treatment, the patient is ineligible.
- 5.2 The participant must have a performance status of 0 by Southwest Oncology Group criteria (see Section 10.3).
- 5.3 The participant must be able and willing to participate in the full seven years of study treatment.

- 5.4 Participants must have a Digital Rectal Examination (DRE) **WITHIN NORMAL LIMITS** (without induration, asymmetry, prostate nodularity). DRE must be performed within 28 days prior to enrollment.
- 5.5 The specimen for PSA must be drawn within 28 days prior to enrollment and sent to the Central Laboratory Facility (CLF). For participants with prostatitis and/or other clinical situations expected to raise the PSA value, it is recommended that enrollment be postponed for two months following resolution of the clinical condition.
- 5.6 Individuals previously diagnosed with prostate cancer or Prostatic Intraepithelial Neoplasia (PIN) are ineligible.
- 5.7 Individuals are ineligible if they have a prior history of malignancies other than basal or squamous cell carcinoma of the skin within the past five years. Individuals are eligible if they have had a prior malignancy but have had no evidence of disease for at least five years prior to registration.
- 5.8 Individuals must not have received prior finasteride or anabolic steroids for any reason. Individuals must not have received prior hormonal therapy, chemotherapy, biologics or radiotherapy as treatment for cancer.
- 5.9 Individuals must not be in urinary retention.
- 5.10 Individuals desiring immediate medical or surgical treatment of urinary obstructive symptoms are ineligible. Individuals must not have had a transurethral resection of the prostate (TURP) less than six months prior to enrollment.
- 5.11 Individuals with severe prostatism as manifested by an AUA symptom score of 20 or greater are ineligible.
- 5.12 Individuals currently receiving anticoagulation therapy (e.g., coumadin) are ineligible. Individuals currently taking aspirin as anticoagulation therapy are eligible.

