**Final Enrollment Criteria**

- 5.22 Participants must have a PSA (prostate specific antigen) performed with monoclonal assay (as determined by the CLF from the specimen drawn at the time of enrollment) 3.0 ng/ml.
- 5.23 Participants with an increase of more than two toxicity grades over the baseline grade for symptoms of impotence, loss of libido, and ejaculate volume at the end of the three month enrollment period are not eligible for final enrollment (randomization). These toxicities must be assessed using the Supplemental Toxicity Criteria in Section 8.2 of this protocol. Participants with other Grade 2 or greater toxicities (as defined by the Southwest Oncology Group Toxicity Criteria) at the end of the three month enrollment period are ineligible for final enrollment (randomization). Dermatologic toxicities must be < Grade 3 for final enrollment.
- 5.24 Participants who fail to meet the enrollment medication adherence criteria are ineligible for final enrollment (randomization).

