**6.0 STRATIFICATION/RANDOMIZATION SCHEME**

- 6.1 Participants will be described by: age (55 - 59 vs 60 - 64 vs 65) at enrollment, race (African-American vs other), and positive family history of prostate cancer in a first-degree relative (yes vs no).
- 6.2 Participants will be randomized to receive finasteride or a matched placebo. (See Study Manual for detailed enrollment and randomization procedures.)

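### Section 11.9 adjusts the primary model for stratification factors that the protocol never names; the covariates should be listed, with baseline PSA among them

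*Supplement*

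**What the plan says.** Section 11.9 defines the primary test as the arm coefficient in a logistic regression for prostate cancer, and fixes the other terms by reference: "The logistic regression model will include covariates for all stratification factors except the Study Center". It lists no covariates itself.

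The place to look them up is Section 6.0, whose heading still mentions stratification. The text of 6.1, however, reads "Participants will be described by: age (55 - 59 vs 60 - 64 vs 65) at enrollment, race (African-American vs other" and goes on to first-degree family history. Amendment #4 explains this wording: it states that "the factors outlined here are descriptive factors rather than stratification factors". Section 6.2 says only that men are randomised to finasteride or matched placebo, and adds "See Study Manual for detailed enrollment and randomization procedures".

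Baseline PSA is available for every randomised man. Section 5.5 states "The specimen for PSA must be drawn within 28 days prior to enrollment and sent to the Central Laboratory Facility", and Section 5.22 makes the central result a condition of randomisation. It is listed neither in 6.1 nor in 11.9.

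Section 11.14 does use age, race, family history, gland size and laboratory data to model the probability of cancer at seven years, but as a secondary analysis.

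**The concern.** The covariate set of the single confirmatory test is defined by pointing to a list that the current protocol does not contain. Study Center is the only stratification factor that 11.9 mentions, and it is excluded. Two analysts could follow 11.9 in good faith and fit different models: one with the arm term alone, the other with arm plus age group, race and family history. With one primary test at 5% two-sided and no interim analysis of the outcome, that choice should not be open when the data are unblinded.

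A second, smaller point follows. If the sentence has to be rewritten anyway, the measurement most likely to sharpen the comparison is already in the database. Section 11.1 itself describes PSA as a marker of growing importance for prostate cancer incidence, and the baseline value precedes any finasteride.

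**Working it through.** **1. What the covariate list contains on each reading.**

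| Reading | Terms in the primary model |
|---|---|
| Literal (6.1 factors are descriptive only) | arm |
| By intent (6.1 factors were meant) | arm, age group, race, family history |
| Study Manual names strata | unknown from the documents |

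**2. The plan's own power figure.** Section 11.10 gives 92.1% for 60% of 9,000 men biopsied (5,400 per arm), a placebo rate of 6%, 5% contamination and 14% nonadherence. The unadjusted difference of 30% gives p1 = 0.06 × 0.70 = 0.042. By the formulas of Section 11.7:

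- p0r = 0.95 × 0.06 + 0.05 × 0.042 = 0.0591
- p1r = 0.14 × 0.06 + 0.86 × 0.042 = 0.04452
- adjusted difference = (0.0591 − 0.04452)/0.0591 = 24.7%, as stated

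The two-sided 5% two-proportion formula gives 92.8%, or 92.15% with continuity correction, which matches 92.1%. It contains no covariates, so the stated power is the same whichever model is fitted.

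**3. What adjustment adds at these rates.** The documents give no covariate effects or prevalences, so these are assumptions: three age groups of about one third each, 5% African-American, 15% with a family history, log PSA standard normal. There were 1,500 simulated trials per row with 5,400 men per arm, and the three models were fitted to the same data. Odds ratios are per age step / race / family history / SD of log PSA.

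| Assumed odds ratios | Arm only | + age, race, family history | + baseline PSA |
|---|---|---|---|
| 1.2 / 1.3 / 1.3 / 1.5 | 92.0% | 92.3% | 92.6% |
| 1.4 / 1.8 / 1.8 / 2.0 | 93.2% | 93.2% | 94.3% |
| 1.5 / 2.0 / 2.0 / 3.0 | 92.4% | 93.1% | 94.9% |

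Monte Carlo SE is about 0.7 points per figure. The three 6.1 factors add 0 to 0.7 points. All four covariates together add 0.6 to 2.5 points, most of it from PSA. The mean size of the arm z statistic shows the same: 3.36, 3.41 and 3.36 with arm only; 3.37, 3.42 and 3.38 with the three factors; 3.39, 3.48 and 3.53 with PSA as well.

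**4. A less favourable base.** With a 25% unadjusted difference (p1 = 0.045), 5% contamination and 10% nonadherence, p0r = 0.95 × 0.06 + 0.05 × 0.045 = 0.05925 and p1r = 0.10 × 0.06 + 0.90 × 0.045 = 0.0465. The formula power is 84.2%. Two sets of paired simulations used one baseline predictor with log odds ratio 0.5, 0.8 or 1.0 per SD (odds ratio about 1.65, 2.2, 2.7). One gave gains of 0.6, 2.0 and 1.4 points (paired SE 0.4 to 0.5). The other, with 2,500 trials per setting, gave 1.0, 1.4 and 2.3 points (paired SE 0.3 to 0.4). A predictor with no effect cost nothing.

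**5. Can the choice of model change the verdict?** In the 2,500-trial simulations, the adjusted and unadjusted tests disagreed about p < 0.05 in roughly 3 to 5% of trials. That is for one predictor of the strength just given. The three 6.1 factors move the z statistic much less (step 3), so disagreement between the two readings of the present text should be rarer, but it is possible near the threshold.

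**The case against.** The best defence is that the gap may be only apparent. The Study Manual holds the randomisation procedures and may name strata. Section 11.9 presupposes factors besides Study Center, Section 6.0 keeps its heading, and the diet study in Appendix 19.7 controls for the same three variables, so intent can be guessed. This stands as a limit on certainty. A reader might infer that the primary model is provably empty; with the Manual unseen, the documents show only that the protocol does not say. But 11.9 does not send the reader to the Manual for its covariates, and the primary model should be readable from the protocol.

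The defence is also right that little hangs on adjustment. Randomisation makes the unadjusted test valid. With 5,400 men per arm, and leaving selective missingness aside, the standardised imbalance in a covariate has SE √(2/5,400) = 0.019, so it lies within about 0.04 SD 95% of the time. Even at a log odds ratio of 1.0 per SD, that shifts the arm log odds ratio by about 0.04, against an effect of 0.26 at 5.925% versus 4.65%.

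Baseline PSA is a recommendation, not part of the inconsistency: it was never a 6.1 factor. Section 7.2 bars men with PSA above 3 ng/ml from randomisation, which narrows its range and may weaken it as a predictor.

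Two further inferences go too far. One is that the baseline data are wasted; Section 11.14 uses them in secondary models. The other is that adjustment would repair the loss of about 40% of endpoints. Section 11.4 already treats comparability of that loss as a critical assumption to be monitored. Adjustment would help only so far as the chosen covariates explain the loss, and no figure supports a benefit.

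**Conclusion.** The point holds as a gap in specification with a free improvement attached. On the protocol's own text, the covariates of the primary test are not identified, and at least two models are consistent with 11.9. Validity and the stated power are not at risk. What is at stake is a post hoc choice between models that could matter if the result falls close to 5%.

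The efficiency gain is modest: close to zero from age, race and family history, and roughly 0.5 to 2.5 power points with baseline PSA. That range rests on assumed odds ratios of about 1.5 to 3 per SD for PSA, on assumed covariate prevalences, and on 5,400 evaluable men per arm. If PSA predicts weakly within the eligible range, the gain falls towards zero and there is no loss. The change is worth making because it is nearly free, not because the trial depends on it.

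**What to change.** In Section 11.9, replace the reference to stratification factors with a named list: age at enrollment, race (African-American vs other), first-degree family history of prostate cancer (yes/no) and log baseline PSA from the central laboratory. State whether age enters in the 6.1 groups or as a continuous term. Fix this before the arms are compared.

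Report the unadjusted comparison alongside. The power calculation refers to it, and the adjusted odds ratio is conditional on the covariates. At the 11.10 rates, the marginal log odds ratio is ln[(0.04452/0.95548)/(0.0591/0.9409)] = −0.30, while the conditional values in the three simulated settings were −0.30, −0.31 and −0.33.

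If the sponsor prefers an unadjusted primary test, or the three 6.1 factors only, saying so outright also closes the gap but forgoes the gain from PSA. Either way the cost is one sentence of analysis text. All four variables are already collected before randomisation.
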